1. LIST OF ABBREVIATIONS

AE	Adverse event
ALT	Alanine aminotransferase
AST	Aspartate aminotransferase
ANOVA	Analysis of variance
ATC	Anatomical Therapeutic Class
BQL	Below limit of quantitation
BUN	Blood urea nitrogen
CI	Confidence Interval
C _{max}	Maximum serum concentration
CFR	Code of Federal Regulations
CRF	Case report form
DVT	Deep vein thrombosis
EBV	Estimated blood volume
ECG	Electrocardiogram
FDA	Food and Drug Administration
FFP	Fresh frozen plasma
GCP	Good Clinical Practice
HBsAg	Hepatitis B surface antigen
Hct ₀	Hematocrit at -1 h before surgery
Hct _f	Hematocrit at 48 h after wound closure
Hct _{av}	Hematocrit average
HCV	Hepatitis C virus
IC	Informed consent
IRB	Institutional Review Board
MedDRA	Medical Dictionary for Regulatory Activities
mg	Milligram(s)
MI	Myocardial infarction
mL	Milliliter(s)
OTC	Over-the-counter
PK	Pharmacokinetic(s)
R	Reference formulation
T	Test formulation

RLD	Reference Listed Drug
RBC	Red blood cell
WBC	White blood cell
SAE	Serious adverse event
TEAE	Treatment-emergent adverse events
V _L	Volume of blood loss

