1. Total Blood Loss based on changes in hemoglobin (Blood loss will be calculated by Nadler's and Gross's formulae from the time of admission to hospital until discharge; Hemoglobin and hematocrit concentrations will be measured pre-operatively, post-operatively, and at 24 h and every 24h thereafter until discharge).
2. Incidence of autologous or allogenic blood transfusion, including red blood cells and coagulation components (such as fresh frozen plasma and platelets).

The Secondary endpoints include assessment of:

1. Total Measured Blood Loss (measured intra-operatively and for up to 24 hours post-operatively and every 24 hours up to discharge when the two subfascial drains are removed). Total Measured Blood Loss will be estimated as 3 times cell saver.
2. Number of patients with symptomatic anemia (such as tachycardia, hypotension, presyncope) of <8.0 g/dL hemoglobin, or any hemoglobin <7.0 g/dL, precipitated transfusion.
[Alternatively, allogenic blood transfusion will be considered for hemoglobin <9 g/dL intraoperatively or <8 g/dL post-operatively]
3. Number of patients with adverse events related to tranexamic acid such as confirmed deep vein thrombosis (DVT), pulmonary embolism (PE), or seizures.
4. Other outcomes will include functional recovery, duration of hospital stay, and wound

complications (infections, hematomas, and other complications related with surgery).

**Safety
Assessments:**

Safety assessments will include monitoring of AEs, and functional recovery assessments, wound complications, length of hospital stay, blood loss, and transfusions.

**Statistical
Methods:**

The primary efficacy variables and continuous secondary efficacy variables will be analysed using Analysis of Covariance (ANCOVA) where one factor is treatment (TXA vs Placebo) and the other factor is Surgeon. The initial analysis will include the interaction between the two factors in order to assess the similarity of effects across surgeons. Significant interaction effects will occur if (for example), TXA works for some surgeons but not for others. The final efficacy analysis will remove the interaction term and control for overall differences between surgeons.

Adverse events will be categorized using MedDRA codes. The TXA and placebo groups will be compared using Fisher exact tests of the number of patients with each category of adverse events. The total number of reported adverse events will also be presented.

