8.4. Randomization and Blinding

When the subjects meet admission criteria and provide written informed consent, they will receive a subject number and be randomized by subject number into one of two treatment arms. They will receive either tranexamic acid or normal saline according to the randomization schedule. The randomization schedule will be generated prior to study initiation by a statistical programmer. The pharmacy will perform and document the randomization.

Subjects will be treated according to a randomization schedule prepared prior to the start of the study. The investigator site personnel as well as Exela personnel involved in the monitoring or conducting of the trial will be blinded to the trial drug codes (or kit codes), except in the case of an emergency. Trial drug codes will not be available to the above personnel until after the completion of the trial and final data review.

An individual decoding unit containing emergency identification of the kit contents will be provided for each kit.

- i. This decoding unit must not be opened unless an actual emergency occurs. The investigator should also make a careful note of the date, time of opening, and the reason.
- ii. In the event that a decoding unit is opened, the Exela monitor must be notified immediately by the investigator.
- iii. At the conclusion of the trial, all decoding units are to be returned to Exela together with unused drug supplies.

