10.2.3. Specimen Preparation, Handling, and Storage

Blood samples for hemoglobin measurement will be collected prior to start of procedure, at the end of the procedure, at 24 h, and every 24 h thereafter until discharge. Hematocrit analysis will also be conducted on all collected blood samples.

Blood lost during surgery will be collected by subfascial Hemovac drains at the incision site into canisters containing heparinized saline. Volumes collected will be recorded post-surgery and every 24 h thereafter until discharge and removal of the two subfascial drains.

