10.3. Study Schedule

10.3.1. Screening

Prior to surgery, subjects will provide written informed consent and will then undergo pre-operative data collection/screening, including:

- Inclusion Exclusion criteria assessment
- Diagnosis leading to surgery
- Planned procedure

-
- Schwab Curve type and coronal curve magnitude (Cobb angle)
 - Patient age and demography
 - Height, Weight, and Body Mass Index
 - Number of units of autologous blood donation
 - CBC: Hb/Hct/WBC/platelet count (post-autologous donation)
 - Coagulation Profile: PT/PTT/INR
 - Medical History and Medication Use
 - History of Previous Spine Surgery
 - Drug / Alcohol / Tobacco Use
 - Medication Allergies
 - Pregnancy testing (females only)

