10.5. Efficacy Assessments

The primary objectives of this trial are to assess:

1. Total Blood Loss (based on hemoglobin changes).
2. Incidence of autologous or allogenic blood transfusion, including red blood cells and coagulation components (such as fresh frozen plasma and platelets).

Total Blood Loss will be determined using Gross's formula¹¹ as follows:

$$V_L = EBV \times \left(\frac{Hct_0 - Hct_f}{Hct_{av}} \right)$$

Where V_L is the volume of total calculated blood loss, EBV is the estimated blood volume from Nadler's formula, Hct_0 is the hematocrit before surgery, Hct_f is the hematocrit at 24 h or discharge/48 h after wound closure and Hct_{av} is the average of Hct_0 and Hct_f .

Nadler's formula¹² is,

Male: $0.3669 \cdot (\text{height})^3 + 0.03219 \cdot (\text{weight}) + 0.6041$, and

Female: $0.3561 \cdot (\text{height})^3 + 0.03308 \cdot (\text{weight}) + 0.1833$,

where, height is in meters and weight is in kilograms.

Secondary efficacy objectives include assessment of:

1. Total measured blood loss (measured intra-operatively and for up to 24 hours post-operatively and every 24 hours up to discharge when the two subfascial drains are removed). Measured Blood Loss will be estimated as 3 times Cell Saver.
2. Number of patients with symptomatic anemia (such as tachycardia, hypotension, presyncope) of <8.0 g/dL hemoglobin, or any hemoglobin <7.0 g/dL, precipitated transfusion. *[Alternatively, allogenic blood transfusion will be considered for hemoglobin <9 g/dL intraoperatively or <8 g/dL post-operatively]*
3. Number of patients with adverse events related to tranexamic acid such as confirmed deep vein thrombosis (DVT), pulmonary embolism (PE), or seizures.
4. Other outcomes will include functional recovery, duration of hospital stay, and wound complications (infections, hematomas, and other complications related with surgery).

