11.4.2. Analysis of Primary Efficacy Endpoint(s)

The primary efficacy variable will be total blood loss as described in Section 10.1. Since blood loss will be measured up to 24 hours after surgery and over the entire period of hospitalization, the primary measure will be the 24-hour level. Blood loss at later time-points will only be considered significant if the 24-hour measure has also reached statistical significance. Due to the hierarchical structure of this analysis, no adjustment for multiplicity will be performed.

The primary efficacy variables and continuous secondary efficacy variables will be analysed using Analysis of Covariance (ANCOVA) where one factor is treatment (TXA vs Placebo) and the other factor is Surgeon. The initial analysis will include the interaction between the

two factors in order to assess the similarity of effects across surgeons. Significant interaction effects will occur if (for example), TXA works for some surgeons but not for others. The final efficacy analysis will remove the interaction term and control for overall differences between surgeons.

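### The primary blood-loss ANCOVA contains no covariate; prespecifying estimated blood volume could buy a modest gain in precision at very little cost

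*Combined protocol and SAP*

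**What the plan says.** Section 11.4.2 analyses the primary efficacy variables by "Analysis of Covariance (ANCOVA) where one factor is treatment (TXA vs Placebo) and the other factor is Surgeon". The synopsis repeats this and adds: "The final efficacy analysis will remove the interaction term and control for overall differences between surgeons". Both named terms are factors, and no continuous baseline variable appears. Sections 11.4.7 and 11.4.9 allow covariance analyses only as optional, exploratory work, and name no covariate.

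Section 10.5 defines blood loss as EBV × (Hct₀ − Hct_f)/Hct_av, where "EBV is the estimated blood volume from" Nadler's formula, a function of sex, height and weight.

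The screening list in 10.3.1 includes demography, "Height, Weight, and Body Mass Index" and "CBC: Hb/Hct/WBC/platelet count (post-autologous donation"). Randomization comes afterwards. Section 8.4 says: "When the subjects meet admission criteria and provide written informed consent, they will receive a subject number and be randomized by subject number". The admission criteria include a hemoglobin limit (8.3.2, item 12), so the blood count has to be known before allocation.

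**The concern.** The label promises an adjustment that the model does not contain. As written it is a two-way analysis of variance.

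The omission is more than a matter of wording, because EBV multiplies the outcome directly. If larger patients lose more millilitres at the same fractional loss, that variation stays in the residual error and widens the confidence interval for the treatment effect. At stake is some power and precision that the trial could have from data it already collects. Covariates chosen after unblinding under 11.4.7 or 11.4.9 would yield only an exploratory result. The gain supports the primary test only if the covariates are named in advance.

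**Working it through.** **Inputs from 11.2.** Two-sided alpha 0.05, control mean 2000 mL, SD 1000 mL, 25% reduction (500 mL), 100:50 allocation, 14.7% loss.

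**Reproducing the plan's figure.** With a noncentral t, 64 per group gives 80.1% power and 63 gives 79.5%, so 128 is right for equal arms. The loss is (150 − 128)/150 = 14.7%.

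**Assumptions not in the documents.** There are 8 surgeons (one per site). The 1000 mL is the SD left after surgeon; 11.2 does not say whether it is that or the total SD. At 128 completers the split is 85:43.

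**Break-even.** Let ν = N − 1 − 8 be the residual degrees of freedom and k the number of added covariates. The expected variance of the treatment effect is multiplied by (1 − R²)(ν − 1)/(ν − k − 1), where R² is the share of variance explained beyond treatment and surgeon. Setting this to 1 gives R² = k/(ν − 1).

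- N = 150, ν = 141: 2/140 = 1.43% for two covariates; 1/140 = 0.71% for EBV alone.
- N = 128, ν = 119: 2/118 = 1.69% for two; 1/118 = 0.85% for EBV alone.
- With 24 surgeons the two-covariate figures are 1.61% and 1.96%.

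**How large might R² be?** Suppose loss = EBV × a fraction independent of EBV, with SD 1000 mL in both arms. The common EBV slope is then proportional to the pooled mean loss, (100 × 1500 + 50 × 2000)/150 = 1667 mL, and R² = (1667/1000)² × CV² = 2.78 × CV², where CV is the coefficient of variation of EBV:

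- CV 10%: 2.78 × 0.0100 = 2.8%
- CV 15%: 2.78 × 0.0225 = 6.3%
- CV 20%: 2.78 × 0.0400 = 11.1%

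Simulation agrees with these values. If millilitres lost do not depend on body size, EBV contributes 0%. Two covariates break even at an EBV CV of √0.0143/1.667 = 7.2% (N = 150) or √0.0169/1.667 = 7.8% (N = 128), if only EBV contributes.

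**Power.** The standard error is 1000 × √[(1/n₁ + 1/n₂)(1 − R²)(ν − 1)/(ν − 3)], tested on ν − 2 degrees of freedom. The factor (ν − 1)/(ν − 3) charges for average chance imbalance: 140/138 = 1.0145 at N = 150 and 118/116 = 1.0172 at N = 128. Example at 100:50 with R² = 6.3%: 173.2 × √(0.937 × 1.0145) = 169 mL.

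| Model | 100:50 SE (mL) | 100:50 power | 85:43 SE (mL) | 85:43 power |
|---|---|---|---|---|
| Treatment + surgeon (planned) | 173 | 81.8% | 187 | 75.5% |
| Two covariates, R² = 0 | 174 | 81.2% | 189 | 74.8% |
| R² = 2.8% | 172 | 82.3% | 186 | 76.0% |
| R² = 6.3% | 169 | 83.7% | 183 | 77.5% |
| R² = 11.1% | 164 | 85.5% | 178 | 79.6% |

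Unrounded, the cost when the covariates explain nothing is 81.78 − 81.23 = 0.55 point at 100:50 and 75.50 − 74.77 = 0.73 point at 85:43. Entering EBV alone would cost less.

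**The case against.** The strongest reply is that the plan already adjusts for surgeon, is valid, and needs nothing more; further covariates with no documented R² are a matter of preference. Much of this stands. The gain rests on an assumed spread of EBV and on how loss scales with body size. At an EBV CV of 10% the gain at 100:50 (0.5 point) only matches the loss if the covariates prove useless, so the trade is not clearly favourable there.

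Two further objections stand. Nothing in the documents shows what screening hematocrit would add beyond EBV; the anemia exclusion narrows its range, and no maximum interval from screening to surgery is given. It is therefore optional here. Also, a reader might take the R² range from the control arm alone, with CV of loss 1000/2000 = 0.5, which gives 0.10²/0.25 = 4%, 0.15²/0.25 = 9% and 0.20²/0.25 = 16%. That overstates it by (2000/1667)² = 1.44, because two-thirds of patients are planned to have a mean of 1500 mL. An R² of 20% has no derivation.

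A reader might also infer that Hct₀ is distorted by treatment. The abbreviation list defines it as "Hematocrit at -1 h before surgery", whereas 10.2.3 says "Blood samples for hemoglobin measurement will be collected prior to start of procedure, at the end of the procedure", and the one-hour loading infusion also precedes the procedure. The draw is therefore not clearly before the infusion. But 10.3.3 gives both arms the same volume, so dilution would be equal, and the documents show no route to bias. The ambiguity is only a reason to prefer the screening value if a hematocrit covariate is used.

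None of this removes the core point: EBV is computed for every patient from pre-randomization data and is a multiplier in the outcome.

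**Conclusion.** The point holds as a modest, conditional gain in efficiency. Under the assumptions above, two covariates add 0.5, 1.9 or 3.7 power points at 100:50 and about 0.5, 2.0 or 4.1 at 85:43. The downside is about 0.5 or 0.7 point if they are not prognostic. If 1000 mL is the total SD and surgeon explains some of it, planned power is already higher: 85.6% at 100:50 if surgeon explains an assumed 10%.

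Two stronger readings should be resisted. First, leaving out the covariates does not bias the estimate or invalidate the test, and it does not make the stated sample size wrong. Second, the 75.5% power at 85:43 is not caused by missing covariates. It comes from sizing for equal arms while allocating 2:1, which is a separate matter that adjustment would only partly offset.

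**What to change.** In 11.4.2 and the synopsis, prespecify the final primary blood-loss model as treatment + surgeon + EBV (Nadler's formula). Screening hematocrit may be added, on the understanding that its contribution is unknown. Report treatment + surgeon as a sensitivity analysis. If Hct₀ is preferred to the screening value, the protocol must first state that it is drawn before the loading infusion. Do not adjust for the number of vertebrae actually fused, which is recorded with the surgical data after randomization.

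The cost is one sentence in each place and one or two degrees of freedom, with no new data if the screening hematocrit is used. If the sponsor prefers to keep treatment + surgeon as the primary model, the ANCOVA label should be corrected.

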11.4.3. Analysis of Secondary Efficacy Endpoint(s)

Secondary efficacy variables will include the following.

1. Blood loss measured as 3 times cell saver.

Also included as secondary efficacy variables will be several outcomes normally treated as adverse events.

1. Incidence of symptomatic anemia as defined in Section 10.1.

Categorical secondary efficacy variables will be similarly analysed using multiple logistic regression analyses. If incidences are low, analyses of interaction effects may not be possible and Cochran-Mantel-Haenszel tests will be used instead.

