5. SCHEMATIC OF STUDY DESIGN

CP-006-2017 – Efficacy and safety of tranexamic acid in spinal fusion surgery

- ❖ Study Cohort - > Adult patients over age 18 electively undergoing complex spinal fusion surgery (T2 to pelvis/Sacrum, greater than 4 FSU's (5 vertebral segments or more)).
- ❖ Arm 1 - > Subjects receiving study drug (treat) (n = 100).
- ❖ Arm 2 - > Subjects receiving placebo (control) (n = 50).
- ❖ Sample size - > 150 study subjects; randomized 2:1 Treat / Control
- ❖ Intervention: Arm1 – Surgery plus study drug
Arm 2 – Surgery with placebo

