11.2. Sample Size Determination

Assuming a two-sided alpha level of 0.05, 80% power and estimated mean blood loss of 2000 mL in the control group (with a relatively low estimated standard deviation of 1000 mL due to limitations in the type of surgery and the patient population) a 25% decrease in blood loss in the treated group would require 128 patients (64 per group). Thus, the proposed sample size of 150 patients (100 active and 50 placebo) will allow 14.7% loss to follow-up which should be sufficient considering the relatively small likelihood of loss to follow-up in these patients.

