11.4. Statistical Analysis

11.4.1. General Approach

Data from multiple centers are intended to be combined under this protocol so that an adequate number of patients/subjects will be available for analysis.

Comparability of treatment groups based on demographic and baseline characteristics of the patients/subjects will be evaluated by appropriate statistical tests.

All hypothesis-testing analyses will be performed at the two-sided significance level of 5% ($\alpha=0.05$).

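### Section 11.4.3 switches from surgeon-adjusted logistic regression to CMH only when incidence is low, but the limiting factor is the unstated number of patients per surgeon

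*Combined protocol and SAP*

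**What the plan says.** Section 11.4.2 sets the pattern for continuous variables. Treatment and surgeon are the two factors, a model with their interaction is fitted first, and then "The final efficacy analysis will remove the interaction term and control for overall differences between surgeons".

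Section 11.4.3 carries this over to binary outcomes: "Categorical secondary efficacy variables will be similarly analysed using multiple logistic regression analyses". It lists no other covariates, so the natural reading is the same factors in the same order, on the logit scale. The only way out of logistic regression is this: "If incidences are low, analyses of interaction effects may not be possible and Cochran-Mantel-Haenszel tests will be used instead".

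The section sets no threshold for low, does not say when it is judged, and makes no provision for few patients per surgeon. Symptomatic anemia is the one binary variable it names. Section 11.4.1 holds every hypothesis test to a two-sided 5% level. The synopsis lists 8 sites, and Section 5 gives 100 TXA and 50 placebo patients. The documents do not give the number of surgeons, the expected anemia incidence, whether surgeon is a fixed or random effect, or whether the logistic test is Wald or likelihood ratio.

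**The concern.** A linear model with one indicator per surgeon gives an unbiased treatment difference however many surgeons there are. Maximum-likelihood logistic regression does not: each surgeon adds an intercept estimated from that surgeon's few patients. When those patients are few, the treatment log odds ratio is biased away from zero and its test rejects too often. This depends on stratum size and does not go away when events are common. So the word similarly does not carry over safely from 11.4.2, and the incidence trigger can keep logistic regression in the setting where it performs worst.

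At stake are the true level of the tests on binary secondary endpoints, the size of the reported TXA benefit, and the usefulness of the preliminary interaction step. Because low is undefined, the choice between two tests that give different p-values also stays open until incidence is known.

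**Working it through.** **1. The plan's own figure.** The only calculated design figure is in Section 11.2. The effect is 25% of 2000 mL = 500 mL, with SD 1000 mL. The normal formula gives n per group = 2 × (1.960 + 0.842)² × (1000/500)² = 2 × 7.85 × 4 = 62.8, so 63. The t-distribution version gives 63.77, so 64 per group and 128 in total, as stated; 1 − 128/150 = 14.7%, also as stated. This sizes blood loss only. For binary endpoints the plan gives no error rate beyond the nominal 5%.

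**2. Inputs.** From the documents: 150 patients, 100:50, two-sided 5%, surgeon as a factor. Assumed because not given: 8, 16, 24 or 30 surgeons of equal volume; incidence 30% or 50% (also 10% and 80%); surgeon log-odds SD 0 or 0.7; surgeon as a fixed effect; allocation not stratified by surgeon.

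**3. Models compared.** Logistic: logit P(event) = a_k + b × treatment, with one a_k per surgeon k. CMH without continuity correction: [Σ(x_k − E_k)]² / ΣV_k, where x_k is the number of TXA events for surgeon k, and E_k and V_k are its hypergeometric mean and variance.

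**4. Null rejection rates** at 30-50% incidence (16,000 trials per setting; Monte Carlo SE = √(0.05 × 0.95/16,000) = 0.17 points):

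| Surgeons | Placebo patients each | Logistic Wald | Logistic LRT | CMH, uncorrected | CMH, corrected |
|---|---|---|---|---|---|
| 8 | 50/8 = 6.3 | 5.2-5.5% | 5.6-5.8% | 4.8-5.0% | 2.9-3.3% |
| 16 | 50/16 = 3.1 | 5.8-6.3% | 6.3-6.7% | 4.9-5.0% | 3.0-3.2% |
| 24 | 50/24 = 2.1 | 6.5-7.0% | 7.2-7.5% | 4.8-5.0% | 2.8-3.2% |
| 30 | 50/30 = 1.7 | 7.2-7.8% | 7.6-8.5% | 4.6-5.0% | 2.8-3.1% |

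Further runs, including some with patients falling to surgeons at random, surgeon SD 0.5 and incidence 20% or 40%, gave LRT rates of 5.3-6.6%, 5.6-7.1% and 7.2-7.9% for 8, 16 and 24 surgeons, and Wald rates of 5.0-5.7%, 5.1-6.2% and 6.3-7.0%.

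**5. Incidence is not the driver.** With 8 surgeons the Wald rate is 4.0% at 10% incidence and 5.3% at 80%. With 24 surgeons it is 6.5% at 80% incidence. At 10% incidence it rises from 4.0% to 5.7% as surgeons go from 8 to 30. The rate follows patients per surgeon, and the inflation is present where events are common.

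**6. Odds ratio under a true effect.** At a true OR of 0.50 the median logistic estimate is 0.47-0.48 with 8 surgeons, 0.46 with 16 and 0.43 with 24. On the log scale, from these rounded medians:
- 8 surgeons: ln 0.48 / ln 0.50 = 1.06 to ln 0.47 / ln 0.50 = 1.09
- 16 surgeons: ln 0.46 / ln 0.50 = 1.12
- 24 surgeons: ln 0.43 / ln 0.50 = 1.22

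The effect is therefore overstated by roughly 6-9%, 12% and 20%. The Mantel-Haenszel OR stays at 0.49-0.50. With no true effect the logistic OR is not shifted.

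**7. The interaction step.** This model cannot be estimated if any surgeon-by-arm cell is empty or has all one outcome. At 40% incidence a placebo cell of 6 has all one outcome with probability 0.6⁶ + 0.4⁶ = 5.1%, and a cell of 3 with probability 0.6³ + 0.4³ = 28%. With perfectly even placebo cells alone, the chance of at least one such cell is 1 − 0.949⁸ = 34% for 8 surgeons and 1 − 0.72¹⁶ = 99.5% for 16. Uneven cells and surgeon differences raise this: simulation gives about 72% with 8 surgeons at 40% incidence and 100% with 16 or more. If its LRT is computed anyway, it rejects 10-11% of the time under the null with 8 surgeons and 15-32% with 16-30.

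**The case against.** The strongest reply is that nothing in the documents shows the trial will have many surgeons. With one per site, the main-effects test is within about a point of 5% and the odds ratio moves from 0.50 to 0.47-0.48, little beside the sampling error of a 150-patient trial. This stands, and it limits the size of the point. A reader might infer from the table that the plan's binary tests run at 6-8%. The documents do not support that as a fact of this trial, because it needs roughly 16-30 surgeons. Unequal volumes also soften it: with weights of 1/rank the Wald rate was 4.9-5.6% with 8 surgeons, 5.9-6.3% with 16 and 5.8-6.7% with 30.

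A reader might also infer that the logistic analysis breaks down. That is true of the interaction model only. The treatment-plus-surgeon model failed to give an estimate in at most 0.1% of runs at 30-80% incidence with up to 40 surgeons, and Section 11.4.2 drops the interaction from the final analysis in any case.

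Third, the reason 11.4.3 gives for CMH is that interaction analyses may be impossible. Read by that purpose, the fallback would apply wherever strata are thin. This is a fair reading, but the stated condition is low incidence, and an analyst following the text would stay with logistic regression at 40%.

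Finally, a reader might infer that the test will be picked after seeing unblinded results. The documents do not show this. Overall incidence can be judged blind, and Section 8.4 withholds the codes until after final data review. What remains is that low has no definition and no stated time of decision.

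**Conclusion.** The concern holds in a limited form. The CMH trigger is attached to incidence, while the behaviour of the surgeon-adjusted logistic analysis depends on patients per surgeon, which the documents leave open. The main-effects test rejects about 5-6% with one surgeon per site and about 6-8% with roughly 16-30 surgeons, Wald slightly below likelihood ratio. A true odds ratio is overstated slightly with 8 surgeons and by about a fifth on the log scale with 24. The preliminary interaction model is unusable in most trials at any plausible surgeon count.

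These sizes rest on assumed surgeon counts, assumed incidences and a fixed surgeon effect; a random effect was not simulated and the documents do not exclude one. The point covers the binary secondary efficacy endpoints, of which symptomatic anemia is the one named. It does not touch the blood-loss ANCOVA. It is a cheap improvement to the plan and does not threaten the trial's main result.

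**What to change.** Replace the two sentences on categorical variables in Section 11.4.3 with: *Each binary secondary efficacy endpoint will be tested once by the Cochran-Mantel-Haenszel test stratified by surgeon, without continuity correction, regardless of incidence, and reported as the Mantel-Haenszel odds ratio and risk difference with 95% CI; event rates by surgeon will be shown descriptively.* State the number of surgeons. Drop the logistic interaction model. If covariate adjustment is wanted, add conditional logistic regression stratified by surgeon as supportive only.

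The continuity clause matters, because the corrected test runs at about 3% and would give power away.

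The cost is two sentences, using the plan's own fallback method. The main test then takes no continuous covariate. Nominal power falls by about 1 to 6 points with 8-24 surgeons at a true OR of 0.50. With 30 surgeons, 50% incidence and a true OR of 0.40 it was 59.1% for CMH against 66.3% (Wald) and 67.3% (LRT), a loss of 7-8 points. Part of that gap is not real power: in the matching null setting the logistic tests reject 7.8% and 8.5%, against 5.0% for CMH.
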